6.3.2.6. HADS questionnaire

Definition

The Hospital Anxiety and Depression Scale (HADS) is a fourteen-item scale that generates ordinal data. HADS is composed by seven items relate to anxiety and seven relate to depression. This patient-reported outcome measure was specifically developed to avoid reliance on anxiety/depression aspects which are also common somatic symptoms of illness, such as fatigue and insomnia or hypersomnia.

The HADS consists of two sub-scores: the HAD-A for anxiety and HAD-D for depression. For each sub-score, each related item is rated on a 4-point scale (from 0 to 3 points) as reported below.

The HAD-A sub-score for anxiety will be computed considering the following 7 items:

1. Item 1-A. *I feel tense or 'wound up'*: scored as 'Most of the time' = 3 to 'Not at all' = 0.
2. Item 3-A. *I get a sort of frightened feeling as if something awful is about to happen*: scored as 'Very definitely and quite bad' = 3 to 'Not at all' = 0.
3. Item 5-A. *Worrying thoughts go through my mind*: scored as 'A great deal of the time' = 3 to 'Very little' = 0.
4. Item 7-A. *I can sit at ease and feel relaxed*: scored as 'Not at all' = 3 to 'Definitely' = 0.
5. Item 9-A. *I get a sort of frightened feeling like 'butterflies' in the stomach*: scored as 'Very often' = 3 to 'Not at all' = 0.
6. Item 11-A. *I feel restless as if I have to be on the move*: scored as 'Very much indeed' = 3 to 'Not at all' = 0.
7. Item 13-A. *I get sudden feelings of panic*: scored as 'Very often indeed' = 3 to 'Not at all' = 0.

The HAD-D sub-score for depression will be computed considering the following 7 items:

1. Item 2-D. *I still enjoy the things I used to enjoy*: scored as 'Hardly at all' = 3 to 'Definitely as much' = 0.
2. Item 4-D. *I can laugh and see the funny side of things*: scored as 'Not at all' = 3 to 'As much as I always could' = 0.
3. Item 6-D. *I feel cheerful*: scored as 'Never' = 3 to 'Most of the time' = 0.
4. Item 8-D. *I feel as if I am slowed down*: scored as 'Nearly all the time' = 3 to 'Not at all' = 0.
5. Item 10-D. *I have lost interest in my appearance*: scored as 'Definitely' = 3 to 'I take just as much care as ever' = 0.

| | |
|--|----------------------------------|
| | Statistical Analysis Plan |
| | Sponsor: Novartis |
| | Protocol: CRTH258AIT04 |

6. Item 12-D. I look forward with enjoyment to things: scored as 'Hardly at all' = 3 to 'As much as I ever did' = 0.
7. Item 14-D. I can enjoy a good book or radio or television programme: scored as 'Very seldom' = 3 to 'Often' = 0.

The sum of the rating of the seven anxiety items will provided the HAD-A sub-score while the sum of the rating of the seven depression items will provided the HAD-D sub-score.

Each sub-score ranges from 0 to 21 points: scores ≥ 11 indicate the presence of an anxious or depressive disorder, scores between 8-10 points are borderline abnormal, and scores ≤ 7 indicate that an anxious or depressive disorder is not present.

Analysis methodology

Each HADS item will be summarized at each visit (i.e., Baseline and Week 48) providing absolute and relative frequencies of each level answer.

HAD-A and HAD-D score will be summarized at each visit by means of descriptive statistics for continuous variable together with absolute changes from baseline. A paired t-test or Wilcoxon signed rank test, based on data distribution, will be used to test the HAD-A and HAD-D score difference at Week 48 vs Baseline.

In addition, HAD-A and HAD-D will be evaluated according to the following categories:

- **Normal:** Score ≤ 7 points that indicates disorder not present
- **Borderline abnormal:** Score between 8-10 points
- **Abnormal:** Score ≥ 11 points that indicate the presence of anxious or depressive disorders

A shift table based on this classification will be provided to compare HAD-A and HAD-D at Week 48 respect to Baseline considering patients who completed HAD questionnaire both at baseline and at Week 48.

Data handling rules

No missing imputation will be performed.

Sensitivity of secondary analysis

Not applicable.

| | |
|--|---|
| | Statistical Analysis Plan |
| | Sponsor: Novartis Protocol: CRTH258AIT04 |

6.3.2.7. EQ-5D-5L questionnaire

Definition

The EQ-5D-5L is a standardized widely used instrument for measuring generic health status. It comprises the following five dimensions: mobility, self-care, usual activities, pain/discomfort, and anxiety/depression. Each of the five dimensions comprising the EQ-5D descriptive system is divided into five levels of perceived problems:

- LEVEL 1: indicating no problem
- LEVEL 2: indicating slight problems
- LEVEL 3: indicating moderate problems
- LEVEL 4: indicating severe problems
- LEVEL 5: indicating unable to/extreme problems.

A unique health state is defined by combining one level from each of the five dimensions (example: health state 11111 indicates no problems on any of the five dimensions). A total of 3125 possible health states is defined in this way. EQ-5D-5L health states can be summarized using the 5-digit code or represented by a single summary number (*index value*), which reflects how good or bad a health state is according to the preferences of the general population of a country/region. The EQ-5D-5L index value will be computed considering the Italian Finch et al value set Version 1.1 (updated January 26, 2022) as provided in the online analysis tool of EQ-5D for Italy country (refers to <https://euroqol.org/support/analysis-tools/index-value-set-calculators/>). The EQ-5D-5L index value can be computed only for patients who answered to all 5 dimensions and is computed as follows:

1. A weight is associate based on each dimensions answer considering the weight reported in table below:

| | | Dimensions | | | | |
|--------|-------------------------------|------------|-----------|------------------|------------------|---------------------|
| | | Mobility | Self-care | Usual activities | Pain/ discomfort | Anxiety/ depression |
| Answer | 1: no problem | 0 | 0 | 0 | 0 | 0 |
| | 2: slight problem | 0.051 | 0.046 | 0.050 | 0.047 | 0.044 |
| | 3: moderate problem | 0.064 | 0.056 | 0.064 | 0.088 | 0.109 |
| | 4: severe problem | 0.244 | 0.216 | 0.225 | 0.353 | 0.318 |
| | 5: unable to/extreme problems | 0.329 | 0.257 | 0.255 | 0.408 | 0.322 |

| | |
|--|----------------------------------|
| | Statistical Analysis Plan |
| | Sponsor: Novartis |

Protocol: CRTH258AIT04

2. The utility score is computing summing each assigned weight across 5 domains
3. EQ-5D-5L index value is derived as $1 - \text{utility score}$

For ease, considering a patient with health state 12345 (i.e., patient who reported no problem for mobility, slight problem for self-care, moderate problem for usual activities, severe problem for pain/discomfort and extreme problems for anxiety depression) the utility index is computed as $0 + 0.046 + 0.064 + 0.353 + 0.322 = 0.785$ and consequently the EQ-5D-5L index value is equal to $1 - 0.785 = 0.215$. Of note, the EQ-5D-5L index value can also be negative for some health state (i.e., 55555).

The EQ-5D-5L total score is determined through a Visual Analogue Scale (VAS) and ranges from 0 to 100 with higher scores indicative of a better health status.

Analysis methodology

Each EQ-5D-5L dimension will be summarized at each visit (i.e., Baseline and Week 48) providing absolute and relative frequencies of each level answer.

A graphical representation of each of the 5 dimensions will also be provided to show the frequencies of each level answer at baseline and at Week 48.

EQ-5D-5L index values and EQ VAS values will be summarized at each visit by means of descriptive statistics for continuous variable together with absolute changes from baseline. A paired t-test or Wilcoxon signed rank test, based on data distribution, will be used to test EQ-5D-5L index values and EQ VAS values difference at Week 48 vs Baseline.

Data handling rules

No missing imputation will be performed.

Sensitivity of secondary analysis

Not applicable.

| | |
|--|----------------------------------|
| | Statistical Analysis Plan |
| | Sponsor: Novartis |
| | Protocol: CRTH258AIT04 |

6.3.4. Measurement of Treatment Compliance

As stated in section 6.6.1 “Treatment compliance” of study protocol, the evaluation of the exposure to the study treatment will be performed and it is described in section 6.4.1 of the present document. The compliance with the study treatment will be assessed by the Investigator at each visit. No formal computation of compliance will be applied since the route of administration necessarily requires the patient’s presence on site and Investigator has to administer the drug to patient. All data collected related to injection will be listed.

6.4. Safety Evaluation

Safety assessments will include complete ophthalmic examination, including IOP measurement prior and after each IVT injection, and vital signs, as well as monitoring and recording type, frequency, and severity for all AEs.

The safety analysis will be performed on the Safety population.

6.4.1. Extent of Exposure

Exposure to the study treatment will be based on the number of IVT injections administered.

The exposure will be summarized as a continuous variable counted the total number of IVT injection taken by each patient. The exposure will be also described as categorical variable considering each injection category (e.g., 1 injection, 2 injection, etc.).

A status of treatment regimen assigned to patient will be described. Considering the number of patients who reached Week 16 visit, patients will be described according to the first regimen choice (i.e., q12w or q8w) and the evaluation of disease activity will be also provided within each group.

6.4.2. Concomitant medications

Concomitant medications are defined as therapies ending or ongoing after the first brolucizumab administration. Concomitant medications/ surgical and medical procedures will be described by ATC code (2nd level class) and Preferred Term, presenting the number and percentage of patients taking at least one concomitant medication/procedures. In addition, a focus on ocular concomitant medications (i.e., condition reported in the ocular category of PRIOR AND CONCOMITANT MEDICATIONS eCRF page) will be also provided overall and according to the study and fellow eye. Of note, the same medication could be reported for both eye and consequently will be count once for study eye, once for fellow eye and only once in the total column.

| | |
|--|----------------------------------|
| | Statistical Analysis Plan |
| | Sponsor: Novartis |
| | Protocol: CRTH258AIT04 |

A medication with a missing start date will be assumed to be a concomitant medication, unless the stop date is before the first brolucizumab administration date, in which case the medication will be summarized as a prior medication. Medications with start dates before the first brolucizumab administration date and missing end dates or end dates after the first dosing date will be summarized as concomitant medications.

Moreover, surgical and medical procedures administrated to each patient will be described will be described by System Organ Class and Preferred Term, presenting the number and percentage of patients taking at least one surgical or medical procedure. In addition, a focus on ocular surgical and medical procedures (i.e., condition reported in the ocular category of SURGICAL AND MEDICAL PROCEDURES eCRF page) will be also provided overall and according to the study and fellow eye. Of note, the same medication could be reported for both eye and consequently will be count once for study eye, once for fellow eye and only once in the total column.

6.4.3. Adverse Events

Treatment-emergent adverse events (TEAEs) are defined as Adverse Events (AEs) that occurs on-treatment period, i.e., with a start date after or on the same date of first administration of study treatment.

General rules for AE Reporting

TEAEs will be descriptively summarized, whether non-TEAEs will only be listed.

TEAE summaries will be presented by primary SOC and PT sorted in alphabetical order within each SOC using the MedDRA dictionary.

If a patient report more than one TEAE coded to the same PT, in the analysis the patient will be counted only once in the incidence calculation for that PT. Similarly, if a patient has more than one TEAE in the same SOC, the patient will be counted only once in the total number of patients with an TEAE for that SOC.

The following TEAE summaries will be produced:

- General summary of TEAEs including the total number of events and absolute and relative frequency of patients with respectively at least one event of the following categories: TEAEs, treatment-emergent serious adverse events (TESAEs), ocular TEAEs, non-ocular TEAEs, suspected drug-related TEAEs, TEAEs with relationship to ocular injection procedure, TEAEs leading to interruption of treatment (defined as events with Action taken with drug of interest equal to “Drug interrupted”), TEAEs leading to withdrawn of treatment (defined as events with Action taken with drug of interest equal to “Drug withdrawn”), TEAEs leading to study discontinuation, fatal TESAEs.
- Summary of all TEAEs by SOC and PT;
- Summary of all TESAEs by SOC, PT and maximum severity.

| | |
|--|----------------------------------|
| | Statistical Analysis Plan |
| | Sponsor: Novartis |
| | Protocol: CRTH258AIT04 |

- Summary of all suspected drug-related TEAEs by SOC and PT;
- Summary of all suspected drug-related TEAEs by SOC, PT and maximum severity.
- Summary of all TEAEs with relationship to ocular injection procedure by SOC and PT;
- Summary of all TEAEs leading to interruption of treatment by SOC and PT;
- Summary of all TEAEs leading to withdrawn of treatment by SOC and PT;
- Summary of all TEAEs leading to study discontinuation by SOC and PT;
- Summary of all fatal TEAEs by SOC and PT;
- Summary of all TESAEs by SOC and PT;
- Summary of all TESAES by SOC, PT and maximum severity.

In addition, focusing on ocular TEAEs, a general summary of these events and their description by SOC and PT will be also provided overall and according to the study eye and fellow eye. Of note, the same medication could be reported for both eye and consequently will be count once for study eye, once for fellow eye and only once in the total column.

Listings of deaths, fatal TEAEs, non-fatal TESAEs, suspected drug-related TEAEs, TEAEs with relationship to ocular injection procedure, TEAEs leading to interruption of treatment, TEAEs leading to withdrawn of treatment, TEAEs leading to study discontinuation will be provided. A listing of all non-treatment emergent adverse event will be also described.

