4.5 Risks and benefits

The risk to participants in this trial may be minimized by compliance with the eligibility criteria and study procedures, as well as close clinical monitoring.

Based on the results of phase III studies HAWK and HARRIER (Dugel et al., 2020), brolucizumab (Beovu®) has been recently approved in US and EU for the treatment of wAMD

at the recommended dose of 6 mg, administered by IVT monthly injection for the first three doses, followed by IVT injections every 8 or 12 weeks, depending on disease activity.

A total of 1088 patients, treated with brolucizumab, constituted the safety population in HAWK and HARRIER, with a cumulative 96-week exposure to brolucizumab and 730 patients treated with the recommended dose of 6 mg. Brolucizumab safety was comparable to aflibercept, with an overall incidence of adverse events balanced across all treatment groups in both HAWK and HARRIER.

For further details on safety information available for brolucizumab (Beovu®) treatment in wAMD, please refer to the Summary of Product Characteristics (Beovu® SmPC, 2020) and to the Investigator's Brochure (IB).

Women of child-bearing potential must be informed that taking the study treatment may involve unknown risks to the fetus if pregnancy were to occur during the study, and agree that in order to participate in the study they must adhere to the contraception requirements outlined in the exclusion criteria ([Section 5.2](#)). If there is any question that the participant will not reliably comply, they should not be entered or continue in the study.

Retinal vasculitis (RV) and/or vascular occlusion (RVO), typically in the presence of IOI have been reported following brolucizumab injection. These immune mediated adverse events may occur following the first intravitreal injection. Discontinuation of study treatment for brolucizumab is required in subjects who develop these events. In addition, subjects who experience IOI may be at risk of developing retinal vasculitis (RV) and/or retinal vascular occlusion (RVO) and should be closely monitored.

Based on clinical studies, IOI related adverse events, including retinal vasculitis and retinal vascular occlusion, were reported more frequently in female patients treated with brolucizumab than male patients (e.g. 5.3% females vs. 3.2% males in HAWK and HARRIER, Novartis data on file).

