- fundus (posterior segment) exam, which includes the evaluation of the vitreous, retina, macula, choroid, and optic nerve will be conducted at every scheduled and unscheduled visit by Investigator according to the clinical practice (fellow eye will be examined at the discretion of the investigator). Pupil dilation is to be performed at the discretion of the Investigator. An examination of the peripheral retina must also be performed, to ensure that the intravitreal injection can safely be performed as needed. Posterior segment examination must be performed carefully before each study treatment. The results of the examination including any abnormalities (e.g. vitreous cells/haze, retinal tear/detachment, hemorrhage and vascular occlusion, vasculitis, etc.) should be recorded in the source documents if appropriate. If there are any signs of IOI, vitreous cells and haze should be assessed using National Institutes of Health (NIH) grading system (Nussenblatt et al., 1985). The outcome of the examination will be documented in the source document (e.g., ophthalmic examination tool) and appropriate eCRF page as applicable. Any clinically significant abnormalities of either eye identified prior to signing the informed consent will be recorded on the medical history eCRF page, and on the adverse event page of the eCRF for any findings identified after signing the informed consent.
- intraocular pressure (IOP) measurement. Further details are reported in [Section 8.4.3](#).

Results of these procedures will be recorded as appropriate in the source documents. Clinically significant abnormalities (as judged by the Investigator) should be recorded as an AE in the eCRF.

Instruct the patient to contact the site for any changes in vision or any symptoms of inflammation between scheduled visits. Every effort should be made to bring the subject for immediate examination. In case of unscheduled visits these additional assessments will be documented in the source and appropriate eCRF pages. These images are requested to be uploaded onto the CRC portal.

When IOI, retinal vasculitis, and/or retinal artery occlusion (RAO) is present or suspected during a visit (both scheduled and unscheduled), investigators must perform thorough ophthalmic examination, [REDACTED]

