6.4.6. Other safety parameters

Pregnancy

Considering female patients, at screening a serum pregnancy test should be performed for all women of childbearing potential. The proportion of patients who perform the pregnancy test together with the corresponding results will be provided. For female patients who do not perform pregnancy test the reason will be summarized (i.e., premenarchal, menopause, sterile, other).

| | |
|--|----------------------------------|
| | Statistical Analysis Plan |
| | Sponsor: Novartis |
| | Protocol: CRTH258AIT04 |

Ophthalmic examination:

A complete ophthalmic examination will be performed on the study eye at Screening, Baseline and Week 48 and may be performed at each in-between scheduled visit by the Investigator. At each visit the Investigators have to exclude the presence of any active intraocular inflammation in the study eye. This exam is also to be performed on the fellow eye at Screening and Week 48. Only data related to study eye will be summarized.

The ophthalmic exam may consist of the following:

- Biomicroscopy (slit lamp examination): the proportion of patients with any abnormal signs in anterior chamber (cells/flare) or Vitreous (cells/haze), the proportion of patients with any signs of Intraocular Inflammation (IOI) will be summarized at each visit. Moreover, the severity of anterior chamber cells and flare and the severity of vitreous cells and haze will be summarized considering the following categories:
 - for *Anterior Chamber cells*: 0 (<1), 0.5+ (1-5), 1+ (6-15), 2+ (16-25), 3+ (26-50), 4+ (>50).
 - for *Anterior Chamber flare*: 0 (None), 1+ (Faint), 2+ (Moderate: iris and lens details clear), 3+ (Marked: iris and lens details hazy), 4+ (Intense: fibrin or plastic aqueous).
 - for *Vitreous cells*: 0 (Clear: None), 0.5+ (Few opacities: 1-10 cells), 1+ (Scattered opacities: 11-20 cells), 2+ (Moderate opacities: 21-30 cells), 3+ (Many opacities: 31-100 cells).
 - for *Vitreous haze*: 0 (No haze), 0.5+ (Sometime subtle), 1+ (Permits a better definition of both optic nerve head and the retinal vessels), 2+ (Permits better visualization of the retinal vessels), 3+ (Optic nerve head is visible, but the borders are quite blurry), 4+ (Optic nerve head is obscured).

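### The SAP pre-specifies no grouped, once-per-patient incidence or worst examination grade for intraocular inflammation, retinal vasculitis and retinal vascular occlusion, the risk behind both protocol amendments

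*SAP*

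**What the plan says.** **Why this risk stands apart.** The rationales of both protocol amendments name RV and/or RVO, typically with IOI, as their main reason. Protocol 1.1 describes a causal immune-mediated link, and protocol 9.1.1 makes RV or RVO a ground for stopping study treatment. Protocol 4.5 cites the risk as one combined rate: IOI-related events, RV and RVO included, "were reported more frequently in female patients treated with brolucizumab than male patients (e.g. 5.3% females vs. 3.2% males in HAWK and HARRIER".

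**Adverse event tables (SAP 6.4.3).** "TEAE summaries will be presented by primary SOC and PT sorted in alphabetical order within each SOC using the MedDRA dictionary". If a patient has several events under one PT, "in the analysis the patient will be counted only once in the incidence calculation for that PT"; the same rule applies within a system organ class (SOC). A general summary counts patients with at least one event in broad classes (ocular, serious, drug-related, leading to withdrawal and others). IOI/RV/RVO is not one of them. Two kinds of maximum-severity table are planned: "Summary of all suspected drug-related TEAEs by SOC, PT and maximum severity" and "Summary of all TESAEs by SOC, PT and maximum severity". The second is listed twice.

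**Examination findings (SAP 6.4.6).** "the proportion of patients with any signs of Intraocular Inflammation (IOI) will be summarized at each visit". Cell, flare and haze grades are summarised by category. The top vitreous-cell class is "3+ (Many opacities: 31-100 cells"), whereas anterior chamber cells, flare and vitreous haze all run to 4+.

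**Unscheduled findings (protocol 8.4.2).** "Instruct the patient to contact the site for any changes in vision or any symptoms of inflammation between scheduled visits". Assessments at such visits are to be documented in the source and the eCRF.

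**The concern.** Secondary objective 8 is the safety and tolerability of brolucizumab. The first question a reader of the report will ask is how many patients had any event of the IOI/RV/RVO group and how bad it became. No planned summary table answers it. A patient with IOI followed by RV sits on two PT lines, so the lines cannot be added. The SOC total mixes in unrelated events. A patient with signs at two visits is counted at both, so visit proportions cannot be added either.

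If the grouping is left until reporting, it will be chosen with the events in view: SAP 6.6 already placed ocular adverse event incidence in the interim analysis. The severity tables add a second gap, because a non-serious IOI event not suspected to be drug-related has no maximum-severity table at all.

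**Working it through.** **Inputs.** N = 122 enrolled (SAP 3.1). Cited rates are 5.3% in females and 3.2% in males (protocol 4.5). The documents give no expected figure for this group. The only design precision figure at this N is for the primary endpoint, and it reproduces: 2 × 1.96 × √(0.5 × 0.5/122) = 17.74%. It does not bear on the safety point.

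**1. What PT lines can tell.** If the PT counts are a, b, c, …, then

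max(a, b, c, …) ≤ patients with any event ≤ a + b + c + …

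The overlap between terms decides where the answer lies, and it is not tabulated. With assumed counts and exact (Clopper-Pearson) 95% CIs:

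| PT counts (assumed) | Lowest possible | Highest possible |
|---|---|---|
| 3, 2, 2 | 3/122 = 2.5% (0.5 to 7.0) | 7/122 = 5.7% (2.3 to 11.5) |
| 2, 2, 1 | 2/122 = 1.6% (0.2 to 5.8) | 5/122 = 4.1% (1.3 to 9.3) |

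In each case the same published lines fit proportions that differ by a factor of more than two. The same inequality holds for visit-by-visit IOI proportions, with visits in place of terms.

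**2. Order of magnitude.** With an assumed female share f, expected patients = 122 × [f × 5.3% + (1 − f) × 3.2%]:

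- f = 0.4: 4.9
- f = 0.5: 5.2
- f = 0.6: 5.4
- f = 0.7: 5.7

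At the two cited rates themselves the expectation is 122 × 3.2% = 3.9 and 122 × 5.3% = 6.5. The chance of at least one case is 98.1% and 99.9% respectively, so the row is unlikely to be empty. A grouped row showing 5/122 would read 4.1% (1.3% to 9.3%); a row showing 0/122 would still give an upper limit of 3.0%.

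**3. Severity tables side by side.**

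| Maximum severity by SOC and PT for | Protocol 12.5.2 | SAP 6.4.3 |
|---|---|---|
| all treatment-emergent events | planned | absent |
| suspected drug-related events | not separately specified | planned |
| serious events | not separately specified | planned, listed twice |

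The first of the two serious-event lines directly follows the all-event SOC/PT table, where the all-event severity table would belong, so it is probably a slip. SAP 1.1, which lists departures from the protocol, does not mention it.

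**4. Vitreous cells.** The classes are 0, 1–10, 11–20, 21–30 and 31–100. A count above 100 fits none of them.

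**5. Timing.** The last Week 16 visit sets the interim cut-off of 16 February 2023 (SAP 6.6). Week 48 falls 32 weeks later, on about 28 September 2023. The SAP is dated 28 November 2023. Tables can still be changed before lock, but the data fields probably cannot.

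**The case against.** A reader might infer that the trial will never yield a patient-level incidence or a worst severity for these events. The documents do not support that. Each PT and SOC is counted once per patient, so RV, for example, gets its own patient-level incidence. Maximum severity is planned for drug-related and for serious events. RV and RVO require treatment to stop, so they should also appear in the table and listing of events leading to withdrawal. Protocol 12.5.2 lists adverse events by participant, so about five cases could be counted by hand. All of this stands. What remains is that nothing fixes the grouping in advance, and that the listings named in SAP 6.4.3 cover selected subsets and not all treatment-emergent events.

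The unscheduled-visit worry is also partly met. Clinically significant findings become adverse events and are counted by start date, and SAP 6.4.6 does not say that unscheduled visits are left out. It gives no rule for them. Protocol 10.1.1 asks for a diagnosis in place of separate signs where possible, which limits the scatter across terms but does not merge IOI, RV and RVO.

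A reader might also infer that the SAP should test the sex imbalance, since SAP 6.5 plans no subgroup analysis. Neither document sets an objective by sex, and about five cases can test nothing.

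Finally, the stated endpoint for objective 8 is the incidence of ocular and non-ocular adverse events, and the planned tables deliver that. The point concerns the one risk that changed the protocol, not the endpoint as a whole.

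**Conclusion.** The point holds as a gap in pre-specified summaries. No grouped once-per-patient incidence is planned for IOI/RV/RVO, and there is no any-visit or worst-grade summary of the examination findings. The planned lines only bound the number of affected patients, to 3 to 7 of 122 in the first illustration. The missing all-event severity table is a documentary conflict with protocol 12.5.2 and needs correcting whatever view is taken of the rest.

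The effect is on descriptive safety reporting only; no efficacy conclusion changes. It should be fixed, because the cost is low and the risk is the one the protocol was amended for.

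Assumptions: the PT counts are illustrative, and the female share is not given. The figure of about 5 of 122 is indicative only. It carries rates from sponsor data on file, from trials of up to 96 weeks, into a 48-week study, and the term list and time window behind those rates are not stated. For the same reason a formal comparison with 5.3% and 3.2% should not be inferred; an interval of 1.3% to 9.3% contains both.

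**What to change.** **SAP 6.4.3**

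- Add one study-eye row: patients with at least one treatment-emergent IOI, RV or RVO event. Define it by a PT list drawn from the dictionary, not from the observed terms, and fix the list before lock. Give n/N, a Clopper-Pearson 95% CI (already used in 6.3.2.4), maximum severity and outcome. Any split by sex is descriptive only.
- Replace the first of the two serious-event maximum-severity lines with the table for all treatment-emergent events by SOC, PT and maximum severity, as in protocol 12.5.2.

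**SAP 6.4.6**

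- Add rows for any post-baseline sign of IOI, at scheduled or unscheduled visits, and for the worst cell, flare and haze grade per patient.
- Report vitreous cells above 100 as a separate class if the eCRF captured such values. If it did not, state the limitation; SAP wording cannot recover data that were not recorded.

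**Cost.** A PT list and one or two extra tables. Apart from the vitreous-cell class, everything uses data already collected. The drawback is small counts with wide intervals, more so if split by sex.
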